## 8.2 ALLOCATION AND BLINDING

### 8.2.1 Treatment Allocation

This study is not randomized. Subjects will be enrolled with the ENTACT (Next Generation) Septal Stapler system.

### 8.2.2 Blinding

The study is not blinded.

### 8.3 **STUDY ENDPOINTS**

#### 8.3.1 Primary Endpoint

At the 21-day follow-up visit, the clinician will examine the patient's nasal cavity and will confirm:

- Septum wall straight appearance (yes/no);
- Complete coaptation of perichondrial flaps on septum wall (yes/no);
- Absence of significant local tissue reaction at the staple site (yes/no);
- Absence of hematoma swelling at the staple site (yes/no);
- No need for re-intervention at the surgery site (yes/no);

If all the answers to the questions above are "YES" then clinical success will be inferred (if any answer is "NO" then repair failure will be inferred).

### 8.3.2 Secondary Endpoints

- At the 5, and 42-day follow-up visit, the clinician will examine the patient's nasal cavity and will confirm:
  - Septum wall straight appearance (yes/no);
  - Complete coaptation of perichondrial flaps on septum wall (yes/no);

This document contains information that is confidential and proprietary to Smith + Nephew PLC and Smith + Nephew, Inc. and is intended for use only by Smith + Nephew and its manufacturer. It shall not be reproduced or copied in whole or in part, nor shall the contents be disclosed by any means without prior written permission from Smith + Nephew, nor shall anyone make any use of it that is contrary to the expressed or implied wishes of Smith + Nephew.

Study Protocol	% smith&nephew	
A prospective, multi-center, single arm PMCF study to evaluate the safety and performance of ENTACT™ (Next Generation) resorbable septal staple system for septoplasty	Number: ENTACT.ENT.PRO.SEP.2019.05	
	Version: 2.0, 27Aug2020	
	Page: Page 44 of 94	

- Absence of significant local tissue reaction at the staple site (yes/no);
- Absence of hematoma swelling at the staple site (yes/no);
- No need for re-intervention at the surgery site (yes/no);
- Assess the following intra-operative times for full population and by sub-groups of Septoplasty only cases and Septoplasty and turbinate reduction cases:
  - Total operation time for the procedure: Recorded as time between start of the procedure and when the drapes are removed from the patient, recorded in minutes
  - Time for operative closure with ENTACT Septal stapler: Recorded as time between start of closure to when the stapler was handed back to the scrub nurse, recorded in seconds.
- NOSE score collected at pre-op and all post-operative visits;
- VAS pain collected at pre-op and all post-operative visits.

## 8.3.3 Safety Endpoints

Following are the safety endpoints for this study:

- Device-related re-intervention;
- All adverse events (AEs) occurring from the time of surgery until re-intervention or study completion;
- Device related AEs (ADEs) and serious adverse events (SAE's);
- Device deficiencies (DDs)

All AEs will be categorized in terms of seriousness and relatedness to the study device or to the surgical procedure. All Serious Adverse Device Effects will be further categorized as Anticipated or Unanticipated. The definitions for each of these categories are based on ISO 14155:2011.

This document contains information that is confidential and proprietary to Smith + Nephew PLC and Smith + Nephew, Inc. and is intended for use only by Smith + Nephew and its manufacturer. It shall not be reproduced or copied in whole or in part, nor shall the contents be disclosed by any means without prior written permission from Smith + Nephew, nor shall anyone make any use of it that is contrary to the expressed or implied wishes of Smith + Nephew.

Study Protocol	> ∕ smith&nephew
A prospective, multi-center, single arm PMCF study to evaluate the safety and performance of ENTACT™ (Next Generation) resorbable septal staple system for septoplasty	Number: ENTACT.ENT.PRO.SEP.2019.05
	Version: 2.0, 27Aug2020
	Page: Page 45 of 94

### 8.3.4 Exploratory Endpoints

Exploratory endpoints proposed, but not limited to, the following:

• Number and type of other S+N devices with the turbinate reduction adjunct procedure

### 8.3.5 Balanced Covariates

The inclusion/exclusion criteria will be generalizable and applicable to the widest possible subset of the population needing septoplasty. These criteria will be uniformly applied so as to enroll a cohort of subjects with similar symptoms and clinical requirements. This should maximize the applicability to as many subjects with similar baseline characteristics and help to bolster external validity.

#### 8.3.6 Subject Attrition

Subject attrition due to reduction in sample size required for precision analysis has been accounted for in the sample size calculation so that the estimate of the Confidence Interval (CI) to be obtained will still be valid through the most efficient use of available subjects.

#### 8.3.7 Pre-specification of Statistical Analysis

The primary outcome measure has been pre-specified as well as the type of statistical analysis to be performed to evaluate procedure success rate so as to minimize reporting bias. The precision analysis planned for the study, which includes construction of confidence intervals for the outcome summaries and a pre-defined range in which the 95% CI for the primary outcome are expected to fall within are designed to maximize the validity of the study results.

More detailed information on analyses to be carried out will be incorporated in the Statistical Analysis Plan (SAP) so as minimize any threats to external validity in order to yield clinically relevant estimates of effects and precision.

This document contains information that is confidential and proprietary to Smith + Nephew PLC and Smith + Nephew, Inc. and is intended for use only by Smith + Nephew and its manufacturer. It shall not be reproduced or copied in whole or in part, nor shall the contents be disclosed by any means without prior written permission from Smith + Nephew, nor shall anyone make any use of it that is contrary to the expressed or implied wishes of Smith + Nephew.

Study Protocol	% smith&nephew	
A prospective, multi-center, single arm PMCF study to evaluate the safety and performance of ENTACT™ (Next Generation) resorbable septal staple system for septoplasty	Number: ENTACT.ENT.PRO.SEP.2019.05	
	Version: 2.0, 27Aug2020	
	Page: Page 46 of 94	

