# 5.1 **PRIMARY OBJECTIVE**

The primary objective of this study is to demonstrate clinical success of the ENTACT (Next

Generation) resorbable septal staple system by examining the patient's nasal cavity at the 21

day follow up visit.

This document contains information that is confidential and proprietary to Smith + Nephew PLC and Smith + Nephew, Inc. and is intended for use only by Smith + Nephew and its manufacturer. It shall not be reproduced or copied in whole or in part, nor shall the contents be disclosed by any means without prior written permission from Smith + Nephew, nor shall anyone make any use of it that is contrary to the expressed or implied wishes of Smith + Nephew.

Study Protocol	> ∕ smith&nephew
A prospective, multi-center, single arm PMCF study to evaluate the safety and performance of ENTACT ™ (Next Generation)	Number: ENTACT.ENT.PRO.SEP.2019.05
resorbable septal staple system for septoplasty	Version: 2.0, 27Aug2020
	Page: Page 27 of 94

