## 10.4.2 Analysis of Secondary Endpoints

Nasal cavity assessments at day 5 and day 42 will be summarized and presented as count and percentage of each criterion.

Successful staple deployment at the operative visit will be summarized by count and percentage. A 95% exact confidence interval for a single proportion will be presented for successful staple deployment using the Clopper-Pearson method. The number of staples used and whether the stapler misfired will also be presented.

Total operating room time will be calculated and summarized using descriptive statistics and will be presented descriptively by septoplasty only cases as well as septoplasty and turbinate reduction cases.

Intra-operative time to deploy staples to complete septoplasty, calculated as time between start of closure to when the stapler was handed back to the scrub nurse, will be summarized and presented descriptively by septoplasty only cases as well as septoplasty and turbinate reduction cases.

NOSE score will be calculated and summary statistics will be presented by visit. Change in NOSE score from the pre-operative visit to each post-operative visit will also be presented and an ANOVA model will be used to assess statistical significance.

This document contains information that is confidential and proprietary to Smith + Nephew PLC and Smith + Nephew, Inc. and is intended for use only by Smith + Nephew and its manufacturer. It shall not be reproduced or copied in whole or in part, nor shall the contents be disclosed by any means without prior written permission from Smith + Nephew, nor shall anyone make any use of it that is contrary to the expressed or implied wishes of Smith + Nephew.

Study Protocol	% smith&nephew
A prospective, multi-center, single arm PMCF study to evaluate the safety and performance of ENTACT™ (Next Generation) resorbable septal staple system for septoplasty	Number: ENTACT.ENT.PRO.SEP.2019.05
	Version: 2.0, 27Aug2020
	Page: Page 57 of 94

The VAS Pain score will be summarized by visit. Change in VAS Pain score from the preoperative visit to each post-operative visit will also be presented and an ANOVA model will be used to assess statistical significance.

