## 11. SAMPLE SIZE JUSTIFICATION

The results of a previous clinical study on an earlier generation of the study device found that 92% of subjects had successful fixation of tissue after one week. It is assumed that the study device will perform at least as well as the 92% found previously. The ICH E9 guidance states that power should be greater than or equal to 80%. Therefore based on statistical precision, the recruitment of 36 subjects would provide us with at least 80% probability of obtaining a 2-sided 95% confidence interval, around the estimate proportion of successful fixations of tissue, to within ±11% precision.

With the same assumption of clinical success rate and same precision target, enrolling 36 subjects in ENTACT (Next Generation) will provide probabilities between 78.4% and 90.3% of obtaining the 2-sided 95% confidence interval of the success rate. To allow for a 10% drop out rate, this study will enrol 40 subjects.

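### The protocol relies on a pre-defined range for the primary confidence interval and aims to demonstrate clinical success, but states no range, performance goal or decision rule

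*Combined protocol and SAP*

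**What the plan says.** Section 8.3.7 says that the planned precision analysis includes "a pre-defined range in which the 95% CI for the primary outcome are expected to fall within", and credits this with maximising the validity of the results. Section 5.1 reads: "The primary objective of this study is to demonstrate clinical success of the ENTACT" (Next Generation) system, judged by nasal examination at the 21-day visit. The synopsis carries the same objective.

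Section 8.3.1 defines clinical success for each patient: all five examination items must be satisfied at Day 21. Section 10.4.1 reports the count and percentage of successes with a Clopper-Pearson 95% interval, and adds logistic models for baseline covariates.

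Section 11 takes its assumed rate from a study of an earlier device generation, in which "92% of subjects had successful fixation of tissue after one week". It continues: "It is assumed that the study device will perform at least as well as the 92% found previously". On precision it says that "the recruitment of 36 subjects would provide us with at least 80% probability of obtaining a 2-sided 95% confidence interval" around the estimated proportion, "to within ±11% precision". It also quotes "probabilities between 78.4% and 90.3% of obtaining the 2-sided 95% confidence interval of the success rate". Ten percent dropout takes 36 to 40.

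**The concern.** A range that an interval is expected to fall within needs limits, and a study that sets out to demonstrate something needs a result that would count as not demonstrating it. Neither is given for the primary endpoint. The study is open-label (Section 8.2.2), and Section 10 requires the SAP only before database lock. A range or threshold supplied at that stage could be chosen with the outcomes already known. The data are intended to support CE marking (Section 4.3), so a reader of the report will want to know what 'demonstrated' means and when that was decided.

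The natural place to look for the missing range is Section 11. What is at stake there is whether its figures supply one, and whether the precision it promises holds for the interval that will be reported.

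**Working it through.** **1. Search for a criterion.**
- Section 5.1: an objective with no threshold.
- Section 8.3.1: a per-patient definition only.
- Section 8.3.7: refers to a range and gives no limits.
- Section 10.1: two-sided 5% tests unless otherwise stated, but no null value for the primary proportion.
- Section 10.4.1: estimate, exact interval and covariate models, with no decision rule.
- Section 11: an assumed rate and a precision target.
- Table 4.4.1-1: maximum allowed counts, for complications only.

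No study-level criterion for the primary endpoint is found.

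**2. Reproduce the Section 11 figures.** Inputs: true rate 0.92, half-width at most 0.11, two-sided 95%, X ~ Bin(n, 0.92). With the normal-approximation (Wald) interval, half-width = 1.96·√[p̂(1−p̂)/n]. For n = 36:
- 32/36: 1.96·√(0.8889·0.1111/36) = 0.103, which meets the target.
- 31/36: 1.96·√(0.8611·0.1389/36) = 0.113, which does not.

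So the probability is P(X ≥ 32) = 84.3%. The same steps give P(X ≥ 27) = 78.4% at n = 30 and P(X ≥ 35) = 90.3% at n = 40. These match the stated 78.4%, at least 80% and 90.3%. The two end figures belong to n = 30 and n = 40. Of the interval methods tried (Wald with and without continuity correction, Clopper-Pearson, Wilson, Agresti-Coull, Jeffreys), only the plain Wald interval fits all three. Dropout: 36/0.9 = 40, as stated.

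**3. Same target with the planned interval.** Section 10.4.1 specifies Clopper-Pearson: lower limit = Beta⁻¹(0.025; x, n−x+1), upper limit = Beta⁻¹(0.975; x+1, n−x), half-width = (upper − lower)/2.
- n = 36: 32/36 gives (0.9689 − 0.7394)/2 = 0.115, too wide; 33/36 gives (0.9825 − 0.7753)/2 = 0.104, met. P(X ≥ 33) = 67.5%.
- n = 40: 35/40 gives 0.113, too wide; 36/40 gives 0.104, met. P(X ≥ 36) = 78.7%.

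| Evaluable n | Wald | Clopper-Pearson (planned) |
|---|---|---|
| 36 | 84.3% | 67.5% |
| 40 | 90.3% | 78.7% |

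**4. If ±11% is read as a fixed band (an inference).** 92 − 11 = 81%; the upper end, 103%, is capped at 100% and never binds. Exact lower limits: 33/36 = 77.5%, 34/36 = 81.3%; 37/40 = 79.6%, 38/40 = 83.1%. So 34/36 or 38/40 successes are needed.

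| True rate | n = 36, P(X ≥ 34) | n = 40, P(X ≥ 38) |
|---|---|---|
| 92% | 44.2% | 36.9% |
| 95% | 73.2% | 67.7% |

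The probability passes 50% at a true rate of about 92.6% (n = 36) or 93.4% (n = 40). The lower value at n = 40 is discreteness: two failures are allowed at either size.

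**The case against.** **A descriptive, precision-sized observational PMCF study needs no threshold, and an estimate with an exact interval suits it.** This stands, and it favours the fix: for such a study the word 'demonstrate' and the range sentence are what is out of place.

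**The SAP will supply the detail.** Sections 8.3.7 and 10 do defer detail to it. But Section 8.3.7 describes the range as already pre-defined, and the SAP deadline does not protect against a choice made after outcomes are known.

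**The range is simply the ±11% target.** Section 8.3.7 introduces it as part of the precision analysis, so this is a fair literal reading. A half-width, however, has no location and is not something an interval can fall within. On this reading the target is stated, but the planned interval meets it less often at 36 than Section 11 says.

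**Stronger readings a reader might infer.**
- *That the interval would miss its range more often than meet it.* This needs the inferred 81% edge, the exact interval and a true rate of almost exactly 92%. Section 11 treats 92% as a floor, and the conclusion reverses slightly above it. With the Wald interval behind the sizing, the band is met with probability 67.5% (n = 36) or 60.1% (n = 40) even at 92%.
- *That 81% is the pass mark.* The 92% is a one-week fixation rate, not a rate for the five-part Day 21 composite, so 92 minus 11 has no basis for the primary endpoint.
- *That Day 5 coaptation is the matching outcome to test against 92%.* Section 9.1 links Day 5 to the fixation period, which concerns timing. The protocol does not define the earlier study's fixation outcome or equate it with coaptation, and Section 4.2.1 separately reports 100% one-week coaptation in another series. Nor is an interval at Day 5 ruled out: Section 10.4.2 says these assessments "will be summarized and presented as count and percentage of each criterion", but Section 10.1 allows confidence intervals where appropriate.

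**Conclusion.** The point holds as a gap between what is claimed and what is specified. A pre-defined range is cited as protecting validity and none is stated; the objective is to demonstrate success and nothing defines it at study level. This rests on the text alone.

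The numerical part is secondary. At a true 92%, the planned exact interval meets the ±11-point half-width with probability 67.5% at 36 evaluable subjects, 12.5 points below the stated minimum of 80%, and with 78.7% if all 40 are evaluable. This assumes that precision means half the total interval width. The fixed-band figures in step 4 only illustrate how much depends on unstated choices; they do not show that the study would miss its own range, because the limits of that range are unknown.

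The change should be made. It alters what can be concluded, not how the study is run.

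**What to change.** 1. In Section 5.1 and the synopsis, reword the primary objective as: *to estimate the Day 21 clinical success rate with an exact (Clopper-Pearson) 95% confidence interval.*
2. Delete the sentence on the pre-defined range in Section 8.3.7. Sections 10.1 and 10.4.1 already carry the commitment to confidence intervals.
3. If the sponsor prefers to keep 'demonstrate', state before enrolment a performance goal for the exact lower limit, justified for the Day 21 composite, with the exact probability of meeting it at the assumed rate and at plausible alternatives.

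Do not adopt 81% as the pass rule, and do not set up a formal comparison of Day 5 coaptation with 92%. Where Section 11 keeps its precision statement, it should give the probability for the planned interval (67.5% at 36, 78.7% at 40).

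The first two changes are wording only, with no effect on sample size, visits or data collection. The price is a more modest objective. The third option costs a justified goal, and possibly an unfavourable stated probability at this sample size.

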#### 8.4 METHODS USED TO MINIMIZE BIAS AND MAXIMIZE VALIDITY

#### 8.4.1 Multi-center

The samples from multi-center are more representative than those from single center, and the latter may lead to deviation of study results due to its systematic errors. The required number of cases can be enrolled in a shorter period, and the samples are more representative and the results are more generalizable.

In this study, subjects will be enrolled at multiple sites, utilizing up to 3 US sites. This will reduce the effect of observer bias that might arise at any one investigational site as well as maximize the diversity of subjects treated.

### 8.4.2 Screening of Subjects

In order to eliminate selection bias, the Investigators will continuously screen all subjects. Subject recruitment continues until the completion of subject recruitment.

#### 8.4.3 Investigator Training

Prior to the clinical trial, the clinical research associate (CRA), coordinating with the persons in charge of the study sites, will train the Investigators on the study protocol, making sure they are familiar with the use of investigational medical device, and implement subject enrollment strictly in accordance with the inclusion criteria and exclusion criteria, conduct relevant examinations according to the protocol requirements, also master all new device-related information found during the clinical trial, thus to minimize the interferential factors. The follow-up exams will be delegated to Investigators not involved in the procedure to reduce potential bias by the surgeon.

### 8.4.4 Clinical Trial Monitoring

Detailed monitoring requirements will be documented in the Clinical Monitoring Plan for this study. The monitor is selected and appointed by the Sponsor to conduct a regular on-site monitoring visit, making sure that all contents in the study protocol are strictly followed. The

This document contains information that is confidential and proprietary to Smith + Nephew PLC and Smith + Nephew, Inc. and is intended for use only by Smith + Nephew and its manufacturer. It shall not be reproduced or copied in whole or in part, nor shall the contents be disclosed by any means without prior written permission from Smith + Nephew, nor shall anyone make any use of it that is contrary to the expressed or implied wishes of Smith + Nephew.

Study Protocol	> ∕ smith&nephew	
A prospective, multi-center, single arm PMCF study to evaluate the safety and performance of ENTACT™ (Next Generation) resorbable septal staple system for septoplasty	Number: ENTACT.ENT.PRO.SEP.2019.05	
	Version: 2.0, 27Aug2020	
	Page: Page 47 of 94	

source documents are inspected to ensure consistent contents with the CRF. Monitoring visits will be conducted at the start, during and at the closure of the clinical study in accordance with Smith+Nephew standard operating procedures (SOPs) and the Clinical Monitoring Plan.

## 9. STUDY PROCEDURES

### 9.1 VISITS AND EXAMINATIONS

None of the listed activities are undertaken by Sponsor personnel.

Schedule of Events	Patient screening and		Post-operative patient visits		
	surgery				
	Screening/Pre- Operative ≤ 30 days	Surgery Day 0	FU time point Day 5±2	FU time point Day 21±7	FU time point Day 42±7
Informed Consent	Х	-	-	-	-
Inclusion/Exclusion	Х	-	-	-	-
Demographics: Medical History	Х	-	-	-	-
Operative data (Intra- operative delivery success, intra- operative time to deploy staples to complete septoplasty)	-	х	-	-	-
Discharge data	-	Х	-	-	-
Visual assessment of nasal cavity	-	-	Х	Х	х
NOSE score	Х	-	Х	Х	Х
Visual Analog Scale	Х	-	Х	Х	Х
Concomitant Medications, Procedures	Х	х	х	х	х
Safety assessment (AE/SAE/ADE/DD)	-	Х	Х	Х	X

